##### 12.4.1 Definitions

Subjective Response: Patients who complete at least the questionnaires at baseline (study entry) and at the last study visit will be included for subjective evaluation.

Evaluable for Objective Response: by physical examination and radiological studies as outlined above.

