At the 2nd-week re-evaluation, they will be escalated to the new dose (1mg/kg/day) if the baselines HR and BP are WNL. Patients will have HR and BP noted after first new dose (1mg/kg/day) of propranolol to ensure that the propranolol is tolerated. If the HR and BP are WNL, they will continue on this new dose and re-evaluated in 2 weeks for the 4th-week evaluation. If they have a drop in HR and BP to below normal range, they will be de-escalated and remain on the prior dose (0.5mg/kg/day) until the next visit (week 4).

At the 4th and 6th-week evaluation, their baseline vitals will be evaluated and their propranolol escalated to the next dose (if vitals are WNL) and have their HR and BP assessed after first new dose. Propranolol will stay increased or held at old dose depending on HR and BP after the first new dose as described above. If on re-evaluation in 2 weeks a patient continues to have below normal HR and blood pressure on re-challenge of the escalated dose, they will not be escalated and remain at the last tolerated dose for the remainder of the 8 week period with no further re-challenges. For patients with below normal HR and BP and needed their doses held, they will be reported as AEs.

At each study visit, patients will be asked to complete validated questionnaire to assess for tolerance to propranolol treatment, subjective changes in lymphedema symptoms, and self-reported function and activities of daily living (SF-36, LYMPH—ICF, and LYMPH—ICF—LL) (See attached documents, Appendix 2). Physical examination will include weight and BMI, vitals (HR, BP), and measurement of girth of normal and affected extremity.

MRIs and blood tests will be performed at study entry and study endpoint to assess for changes in lymphedema tissue composition[21-23] in response to propranolol.

Blood draws will be performed at study entry, at the midpoint, and study endpoint to assess for changes in circulating biomarkers in response to propranolol treatment.

Correlative biomarkers assessed will include markers of progenitor, endothelial, lymphatic, macrophage, and adipocyte cells, and expression of beta-adrenergic receptors (Table 3).

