## 11.2 Study Design/ Endpoints (Table 2)

11.2.1 **Study design:** Each patient will serve as his/her own control, for comparison of study questionnaires (subjective) and with changes in the clinical measurements and imaging measurements of the anatomic area affected by lymphatic malformation compared before and after treatment (objective). In our experience, children exhibiting responses to propranolol displayed these within 2 weeks of beginning propranolol treatment, with estimated reduction in the overall volume of the affected area exceeding 20%.

11.2.2 **Primary endpoints:** The primary endpoint will be the tolerability of escalating dosage of propranolol both by subjective reporting (survey instrument) as well as objective measurements of vital signs. Survey instruments include a general quality of life (QOL) and function survey (SF-36), as well as validated survey instruments for patients with lymphedema (LYMPH—ICF, LYMPH—LCF—LL)[38, 39].

11.2.3 **Secondary endpoints:** The secondary endpoints of the study will be both subjective and objective evaluation of the lymphedema after propranolol treatment, as measured by both survey instrument and objective measurements (clinical exam and radiological studies), as well as biological assays from tissues obtained from biopsies.

11.2.3.1 We will determine whether higher doses of propranolol are well tolerated in this patient population. Secondarily, we will measure determine whether higher doses correlate with improvement in lymphedema symptoms and signs, and healing or improvement of skin lesions, if present (reduced lymphatic leakage, reduced bleeding). Skin lesions will be photographed at clinical visits, and daily lymphatic fluid losses estimated by weight measurements.

Using MRI and body composition analysis, we will determine whether propranolol decreases lymphedema, alters edema water content and location (intracellular vs. interstitial), or alters adiposity of affected extremity.

We will study the biologic activity of oral propranolol against lymphedema, by examining the expression of progenitor cell markers, lymphatic endothelial cell markers, beta-adrenergic receptor expression, macrophage markers and detection of adipocyte content of biopsy specimens (see table below). Results will be compared to ultrasound and magnetic imaging data.

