#### 11.3.3 Patient-Reported Outcomes; Symptom Assessment etc.

Patients' self-reported tolerance to propranolol will be assessed using validated quality of life (QOL) health surveys (SF-36, Lymph-ICF, Lymph-ICF-LL) SF-36 is an accepted general health status survey[38, 39]. Lymph-ICF and Lymph-ICF-LL are validated, disease-specific survey instruments for patients with lymphedema that evaluate physical and mental activity, impairments in function and activity limitations related to lymphedema.

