#### 11.5 **Reporting and Exclusions**

All of the patients who met the eligibility criteria (except those who received no propranolol) will be included in the main analysis of the response. All conclusions will be based on all eligible patients.

Sub-analyses may then be performed on the basis of a subset of patients, excluding those for whom major protocol deviations have been identified. However, these sub-analyses will not serve as the basis for drawing conclusions concerning treatment efficacy, and the reasons for excluding patients from the analysis will be clearly reported.

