### **12.0 EVALUATION CRITERIA**

#### 12.1 **Adverse Events**

Any patient who receives the study drug will be evaluable for Adverse Effects. This study will utilize the NIH Common Terminology Criteria for Adverse Events v4.0 (CTCAE) for evaluating adverse events.

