#### 12.4 **Response**

Patients should be re-evaluated for response by clinical examination every 2 weeks. Baseline MRI will be obtained, and an MRI repeated at 8 weeks. Response will be evaluated in this study using quality of life survey instruments, physical examination and radiologic studies (MRI at baseline and 8 weeks).

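### Section 12.4.1 admits only patients with baseline and last-visit questionnaires to the subjective evaluation, which contradicts 11.5 and, if the last visit means Week 8, leaves early stoppers out of the questionnaire results

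*Combined protocol and SAP*

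**What the plan says.** All references are to the combined protocol and SAP.

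- **12.4 and 12.4.1.** Section 12.4 says: "Response will be evaluated in this study using quality of life survey instruments, physical examination and radiologic studies". Under the label Subjective Response, 12.4.1 adds: "Patients who complete at least the questionnaires at baseline (study entry) and at the last study visit will be included for subjective evaluation". The term *last study visit* is not defined.
- **11.5.** "All of the patients who met the eligibility criteria (except those who received no propranolol) will be included" in the main analysis of response, and all conclusions are to rest on all eligible patients.
- **11.2.2.** The primary endpoint is the "tolerability of escalating dosage of propranolol both by subjective reporting (survey instrument) as well as objective measurements of vital signs". The surveys named there are the SF-36 and the two Lymph-ICF forms.
- **1.1.2a and 11.3.3.** Aim 1.1.2a assigns energy, fatigue, dizziness and wheezing to those instruments. Section 11.3.3 says that patients' "self-reported tolerance to propranolol will be assessed using validated quality of life (QOL) health surveys".
- **2.4 and Table 6.** "At each study visit, patients will be asked to complete validated questionnaire to assess for tolerance to propranolol treatment". Table 6 schedules the forms at pre-study and Weeks 1, 2, 4, 6 and 8.
- **12.1.** "Any patient who receives the study drug will be evaluable for Adverse Effects".

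**The concern.** Requiring a last-visit form selects patients on something that happens after treatment starts. Some patients are taken off because they did not tolerate the drug, so a missing final form can be a consequence of the outcome being measured. A mean change computed without those patients tends to look better than the mean over everyone treated.

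The matter reaches beyond a secondary response summary because the protocol reads the same questionnaires as measures of tolerance and names no other set for that reading. Where 12.4.1 and 11.5 give different populations, the choice could also be made after the data are seen. With 15 to 20 patients, one or two exclusions can shift a mean.

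**Working it through.** **1. The plan's own figure.** Section 11.1 expects 15 to 20 patients over 24 months at 8 to 10 a year: 8 × 2 = 16 and 10 × 2 = 20, which agrees. The documents give no power calculation, effect size or dropout rate, so the number of stoppers below is an assumption.

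**2. Who can lack a Week 8 form.**
- Failure at the initiation dose (5.2.2, 14.2.3).
- Two failed challenges at 1 mg/kg/day (14.2.3). Sections 2.3.2.1 and 5.2.2 can be read as holding such a patient at the tolerated dose instead. These passages must be reconciled, since they affect how many patients leave.
- Symptomatic low glucose, or bronchospasm not linked to a URI that persists or needs new treatment (Table 5).
- Refusal of further therapy (10.1).

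Patients who twice fail a later step stay on study (14.2.3), so their Week 8 form is still expected. Section 10.1 asks for follow-up data after therapy stops, but neither it nor Table 6 schedules a questionnaire at stopping.

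As an example, a patient pulled after failed challenges at Weeks 2 and 4 would have been due forms at pre-study and Weeks 1, 2 and 4. On the Week 8 reading, 12.4.1 uses none of them.

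**3. Effect on a mean change.** Let N be the number treated, k the number without a last form, and δ the amount by which stoppers' mean change is worse, in SDs of change.

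Mean over all treated = completers' mean − (k/N) × δ, so the completers-only mean is flattered by (k/N) × δ. I assume δ = 1 and k = 1 to 4. The result scales in proportion to δ.

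**4. The same loss seen as a proportion.** As a limiting case, count each stopper as intolerant and suppose that no remaining patient reports intolerance. Intervals are Clopper-Pearson 95%.

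| N | k | Mean flattered by (SD) | All treated | Last-visit form only |
|---|---|---|---|---|
| 20 | 1 | 0.05 | 5.0% (0.1–24.9) | 0/19, upper limit 17.6% |
| 20 | 2 | 0.10 | 10.0% (1.2–31.7) | 0/18, upper limit 18.5% |
| 20 | 4 | 0.20 | 20.0% (5.7–43.7) | 0/16, upper limit 20.6% |
| 15 | 1 | 0.07 | 6.7% (0.2–31.9) | 0/14, upper limit 23.2% |
| 15 | 2 | 0.13 | 13.3% (1.7–40.5) | 0/13, upper limit 24.7% |
| 15 | 4 | 0.27 | 26.7% (7.8–55.1) | 0/11, upper limit 28.5% |

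**5. Scale.** The standard error of the completers' mean is 1/√(N − k) SD. For N = 20, k = 1, the shift is 0.05/0.229 = 0.22 standard errors. For N = 15, k = 4, it is 0.267/0.302 = 0.88.

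**6. Chance that the question arises.** The probability of at least one stopper is 1 − (1 − p)^N. At an assumed p = 10% it is 79% (N = 15) or 88% (N = 20). At p = 20% it is 97% or 99%.

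**7. The other reading.** If *last study visit* means the last visit attended, a stopper with any post-baseline form is kept, and the shift is close to zero.

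**The case against.** The strongest reply is that 12.4.1 is a response rule. It sits under Response and is labelled Subjective Response, while response of the lymphedema is a secondary endpoint. The population written for toxicity is in 12.1 and covers everyone treated. This stands in part: applying 12.4.1 to tolerability is an inference from shared instruments and the lack of another rule. But 12.1 protects adverse-event counts, not questionnaire scores. And if 12.4.1 concerns response alone, it conflicts directly with 11.5, which also concerns response.

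The second reply is that the term may mean the last visit attended. The text allows this. Week 8 is the more natural reading, because Table 1 places the exit interview there, but the documents do not settle it.

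Third, a reader might infer that everyone who stops for intolerance disappears from the primary endpoint. The documents do not support that. Failures at later steps remain on study, and symptomatic low heart rate or blood pressure can lead to re-evaluation and reintroduction (Table 5). Toxicity rates by dose are still reported (8.4). Nor is the survey component half of everything primary, since the Abstract and Aim 1.1.1 also make QMR validation primary.

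Fourth, it is tempting to simulate patients leaving after a set fall in score and to report a large share of the worsening as lost. No removal that the protocol mandates is triggered by a questionnaire score. Voluntary refusal is the nearest route, so such a figure would reflect its own assumptions and not this trial.

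Finally, 8.4 is not confined to a t-test. It also provides descriptive summaries and a rank-based alternative.

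**Conclusion.** The point holds in a limited form and should be fixed. The contradiction between 12.4.1 and 11.5 is on the face of the text and needs no assumption. Bias in the self-reported tolerability results is conditional on three things: that 12.4.1 governs those results for want of another rule, that *last study visit* means Week 8, and that patients taken off early supply no later form.

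Under those conditions, and with the assumed 1 to 4 stoppers and δ = 1, the flattering of the mean is modest. It is at most about nine tenths of a standard error and may be negligible. The documents do not show that the plan definitely excludes intolerant patients from its primary endpoint, and the point should not be put that strongly.

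**What to change.** 1. Replace the 12.4.1 sentence with wording such as: *The subjective evaluation includes every patient who received propranolol and has a baseline questionnaire and at least one questionnaire completed after the first dose; forms from all scheduled visits are used.* Say whether this set also governs the tolerability reading in 11.2.2 and 11.3.3.
2. Name the analysis. A mixed model over visits is one option, though not essential with 15 to 20 patients. The change to the last available form is a simple alternative, but it mixes doses and times on treatment.
3. Have patients who stop complete the questionnaires already in use at the stopping visit, and add this to Table 6.
4. Report how many treated patients lack a Week 8 form and how many lack any post-dose form, with reasons and last scores. The second group would still fall outside the new set, so the report must show them.
5. Reconcile 12.4.1 with 11.5 so that one population is stated, and define *last study visit* if the term is kept.

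The cost is protocol and SAP wording plus one form for each patient who stops. The other data are already scheduled. The result may look slightly less favourable.

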#### 13.0 **ADVERSE EVENT REPORTING REQUIREMENTS**

Adverse events (AEs) will be graded according to the NIH's Common Terminology Criteria for Adverse Events v4.0 (CTCAE) (Section 5.3):

- Grade 1 Mild AE
- Grade 2 Moderate AE
- Grade 3 Severe AE
- Grade 4 Life-threatening or disabling AE
- Grade 5 Death related to AE

Any life-threatening (grades 4 and 5) adverse events (AEs) should be reported immediately (within 24 hours) to the PI and Data Safety Monitoring Board. All other AEs (grades 1-3) will be reported to the PI, the IRB, and the Data Safety Monitoring Board as soon as possible, but not later than five (5) workdays from first awareness of the problem. Significant AEs include, but are not limited, to:

- a. any death, excluding death due to the progression of the disease, and
- b. the combination of the following 3 conditions:
  - i. Unexpected: any adverse experience that is not identified in nature, severity, or frequency in the consent form, and is not due to the progression of a disease process.
  - ii. Serious: any event that is fatal or life threatening, is permanently or significantly

disabling, requires inpatient hospitalization or prolongation of hospitalization, or any medical event that requires treatment to prevent one of the medical outcomes listed above.

iii. Related/possibly related: as determined by the research team.

The event will be formally reported on the Significant Adverse Event Report Form (Medwatch 3500 Form, Appendix 1). All events that do not meet the criteria of significant or trends as listed in numbers 1 and 2 above, should be recorded in the summary form.

## **14.0 RECORDS, REPORTING, AND DATA AND SAFETY MONITORING PLAN**

### **14.1 Data Safety and Monitoring**

The frequency and severity of all toxicities and/or adverse effects will be tabulated on an ongoing basis and summarized for review under the Data Safety and Monitoring Plan for this study (DSMP) as per the guidelines for the Data and Safety Monitoring Committee of Columbia University. Data for this study will be reviewed and monitored by the PI, as this study is deemed minimal or no more than minor increased over minimal risk. All serious and/or unexpected events will be communicated to the Study Chair and reviewed within 2 working days for consideration of notification, amendment, or immediate study suspension.

### **14.2 Data and Safety Monitoring Plan**

#### **14.2.1 Monitoring mechanisms**

It is the responsibility of the Principal Investigator to oversee the safety of the study at his/her site. This safety monitoring will include careful assessment and appropriate reporting of adverse events, as well as the construction and implementation of a site data and safety-monitoring plan. Medical monitoring will include a regular assessment of the number and type of serious adverse events.

#### Data and Safety Monitoring Board

The PI will oversee the conduct of this trial with an *ad hoc* Data and Safety Monitoring Board. The DSMB will review the progress of the trial following the enrollment of subjects and to ensure that patient safety is not being compromised. We have formed an ad hoc DMSB comprising of a vascular surgeon ([name]), a cardiologist ([name]), and a pediatric hematologist with expertise in vascular malformations ([name]).

### MedWatch 3500 Reporting Guidelines:

In addition to completing appropriate patient demographic and suspect medication information, the report should include the following information within the Event Description (section 5) of the MedWatch 3500 form:

- Treatment regimen (dosing frequency, combination therapy)
- Protocol description (and number, if assigned)
- Description of event, severity, treatment, and outcome, if known
- Supportive laboratory results and diagnostics
- Investigator's assessment of the relationship of the adverse event to each investigational product and suspect medication

### Follow-up information:

Additional information may be added to a previously submitted report by any of the following methods:

- Adding to the original MedWatch 3500 report and submitting it as follow-up
- Adding supplemental summary information and submitting it as follow-up with the original MedWatch 3500 form
- Summarizing new information and faxing it with a cover letter including subject identifiers (i.e. D.O.B. initial, subject number), protocol description and number, if assigned, suspect drug, brief adverse event description, and notation that additional or follow-up information is being submitted (The subject identifiers are important so that the new information is added to the correct initial report)

### Assessing Causality:

Investigators are required to assess whether there is a reasonable possibility that propranolol caused or contributed to an adverse event. The following general guidance may be used.

*Yes:* if the temporal relationship of the clinical event to propranolol administration makes a causal relationship possible, and other drugs, therapeutic interventions or underlying conditions do not provide a sufficient explanation for the observed event.

*No:* if the temporal relationship of the clinical event to propranolol administration makes a causal relationship unlikely, or other drugs, therapeutic interventions or underlying conditions provide a sufficient explanation for the observed event.

For **Investigator Sponsored IND Exempt Studies**, there are some reporting requirements for the FDA in accordance with the guidance set forth in 21 CFR 314.80.

### *Postmarketing 15-Day "Alert Report":*

The Sponsor-Investigator is required to notify the FDA of any fatal or life-threatening adverse event that is **unexpected and assessed by the investigator to be possibly related to the use of propranolol**. An unexpected adverse event is one that is not already described in the Investigator Brochure. Such reports are to be submitted to the FDA (2 copies) at the following address: Central Document Room, [name].

For questions related to safety reporting, contact:

Columbia University/[name].  
[contact]

AND

Columbia University Data and Safety Monitoring Committee of Columbia University  
[name]  
[name]  
[contact]  
[contact]

Adverse Event Reporting Period

The study period during which adverse events must be reported is normally defined as the period from the initiation of any study procedures to the end of the study treatment follow-up. However, any serious treatment emergent adverse events must be reported within 24 hours.

Post-study adverse event

All unresolved adverse events should be followed by the investigator until the events are resolved, the subject is lost to follow-up, or the adverse event is otherwise explained. At the last scheduled visit, the investigator should instruct each subject to report any subsequent event(s) that the subject, or the subject's personal physician, believes might reasonably be related to participation in this study. The investigator should notify the study sponsor of any death or adverse event occurring at any time after a subject has discontinued or terminated study participation that may reasonably be related to this study.

**14.2.2 Frequency of monitoring**

Patients will be monitored and assessed during their study visits (weeks 1, 2, 4, 6, 8). In addition, patients will be encouraged to contact the PI and/or study coordination if they have any issues, concerns, unexpected symptoms to be assessed.

**14.2.3 Stop or change rules**

Patients will be removed from study if they cannot tolerate the initiation dose of propranolol. Patients who failed 2 challenges to escalate to 1mg/kg/day (lowest study dose) will be pulled from the study. Patients who failed 2 challenges to escalate to subsequent doses will be kept at the highest tolerated dose without any further attempts to escalate through the study.

